1.3.4 Device Regulatory Pathway

[figure not shown]
Under 21 CFR 812.3(m), a significant risk device means an investigational device that:

- 1. Is intended as an implant and presents a potential for serious risk to the health, safety, or welfare of a subject,
- 2. Is purported or represented to be for use supporting or sustaining human life and presents a potential for serious risk to the health, safety, or welfare of a subject,
- 3. Is for a use of substantial importance in diagnosing, curing, mitigating, or treating disease, or otherwise preventing impairment of human health and presents a potential for serious risk to the health, safety, or welfare of a subject, and/or
- 4. Otherwise presents a potential for serious risk to the health, safety, or welfare of a subject.

The Noxsano Bandage is not an implantable device nor is it designed to sustain life; in this regard it is clearly not a significant risk device as defined by the FDA. The Noxsano Bandage also does not treat a disease, but does treat wounds which certainly could be considered an impairment of human health. The Bandage does not, in the manufacturer's opinion however, represent a serious risk to the health, safety, or welfare of the study subjects. The study subjects already have non-healing wounds that impair their health. The objective of the study will be to show improved healing relative to established techniques. Subjects will be monitored and returned to established techniques if the Noxsano Bandage fails to improve their healing. No preclinical evidence of significant risk has been demonstrated, and therefore significant risk is not anticipated or expected:

♦ NO is a naturally-occurring species produced by the body during healing as a biosignal, but is absent in chronic wounds.

IRB# 1331496 Page 15 Version 6.0

- ♦ Exogenous delivery replaces the missing NO at levels equivalent to those generated naturally, restoring the wound to its 'natural state.'
- ♦ NO is short lived (1-2 seconds) and therefore does not become systemic. Biological activity is limited to the wound.
- ♦ The level of NO is highly controlled by the electrochemical reaction, thus preventing any risk of overdose.
- ♦ The level delivered to the wound is fixed by the battery voltage and the formulation and cannot be altered by the patient.

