2.4 Secondary Endpoint (Group 2 only)

Standard wound healing techniques generally demonstrate 50% wound healing at 2 months. Therefore, the secondary endpoint for this study is the proportion of wound care patients that have at least 50% improvement in surface area within 2 months of treatment. This information will be used to describe if the study device is equivalent to standard and established techniques.

IRB# 1331496 Page 18 Version 6.0

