3.0 STUDY DESIGN

3.1 Study Design Overview

This study is a prospective, interventional, non-randomized, sequential phase study designed to assess the safety and efficacy of the Noxsano Bandage (study device) in subjects with a diabetic lower extremity ulceration and/or arterial insufficiency lower extremity ulceration.

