5.2 Concomitant Medications

A list of all prescription and over the counter medications, including topical treatments, will be recorded for all subjects at each visit.

Although subjects are excluded from Group 1 if they are on any prescription medications at the time of study initiation, due to the short duration of the procedure period (3 days), subjects who initiate prescription and/or over the counter medications during study participation will continue in the study.

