Group 2 (Wound Care Subjects): The initial device application visit (Day 0) may be combined with the screening/baseline visit. Group 2 subjects will be limited to a maximum wound surface area of $< 25 \text{ cm}^2$, to allow for complete coverage with the largest device size of $6 \times 8 \text{ cm}$. Those with wounds $\geq 25 \text{ cm}^2$, comprising less than 5% of the wound care population, will be excluded. Conversely, we are not limiting minimum wound size, as some of the most complicated wounds are actually under 1 cm^2 .

The standard wound measurement in centimeters using a conventional ruler will be obtained according the The OhioHealth Heart and Vascular Wound Care Center standard protocol prior to the initial device application at Day 0. The standard measurement per the current protocol at the Center for Critical Limb Care will be implemented and a photograph with the conventional ruler in place will be taken.

The study device will be applied to the lower extremity wound site by a trained investigator or sub-investigator. Routine wound care techniques such as debridement will be performed in the usual standard fashion prior to application of the Noxsano Bandage. The SAR questionnaire will be administered by study staff immediately following application of the Noxsano Bandage to assess tolerance, side effects, and/or adverse reactions (App. A).

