9.0 STATISTICAL CONSIDERATIONS

Primary Objective.

Group 1 (Safety): Healthy Volunteers. The initial phase of the study is designed to determine the safety of the study device in normal healthy volunteers without wounds. If there are no issues with tolerance, side effects, and/or adverse reactions in normal healthy volunteers, the second phase of the study will proceed with active wound care subjects.

Group 2 (Efficacy): Wound Care Subjects. The second phase of the study is designed to determine the effectiveness of the study device in wound healing in subjects with active wounds (see Primary Endpoint below), and to determine if the study device is equivalent to standard and established techniques (standard techniques demonstrate 50% wound healing at 2 months).

Primary Endpoint.

The primary endpoint for this study is wound healing (Group 2), as defined by the percent change in wound surface area (surface area is calculated in cm²) from baseline through the active treatment period. Wound care subjects will have the study device applied (and re-applied weekly) until the wound is judged to be healed by the wound care practitioner, for up to 3 months total duration. If after 2 consecutive months of treatment with the study device the wound does not exhibit at least 50% improvement in surface area (cm²), the subject will be returned to standard and established techniques consistent with the wound etiology. We will also determine if the study device is equivalent to standard and established techniques (standard techniques demonstrate 50% wound healing at 2 months).

Statistical Analysis Plan.

Descriptive statistics will comprise the bulk of the statistical analysis. Continuous variables will be reported as means and standard deviations, along with median and minimum/maximum values and compared between baseline and follow-up times using paired t-tests and/ or repeated measures ANOVA. Dichotomous and categorical variables will be reported as frequencies with percentages and compared between follow-up times using Chi-square tests or Kruskal Wallis tests. Imputation techniques will be used to account for missing data. Statistical significance will be set at p<0.05 for all the tests.

IRB# 1331496 Page 41 Version 6.0

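### A result near 50% in ten uncontrolled Group 2 subjects on routine wound care can neither establish equivalence to standard care nor show that the bandage works

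*Combined protocol and SAP*

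**What the plan says.** **Design.** Section 3.1: "This study is a prospective, interventional, non-randomized, sequential phase study". Group 2 is a single arm of 10 (3.2), with no sham and no concurrent standard-care group.

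**Benchmark and endpoint.** Section 2.4 starts from "Standard wound healing techniques generally demonstrate 50% wound healing at 2 months", without a source, and defines the secondary endpoint as "the proportion of wound care patients that have at least 50% improvement in surface area within 2 months of treatment". It then says "This information will be used to describe if the study device is equivalent to standard and established techniques". The Protocol Summary (Objectives) and 2.3 give the same aim, but as something to be determined rather than described. Section 9.0 repeats it under both the primary objective and the primary endpoint: "We will also determine if the study device is equivalent to standard and established techniques".

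**Background care.** Section 5.7, on the initial Group 2 application, says "Routine wound care techniques such as debridement will be performed in the usual standard fashion prior to application of the Noxsano Bandage". Section 5.2 adds "A list of all prescription and over the counter medications, including topical treatments, will be recorded for all subjects at each visit". No section lists wound treatments that are barred while the bandage is in use.

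**A different aim.** Section 1.3.4: "The objective of the study will be to show improved healing relative to established techniques".

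**Analysis.** Section 9.0 is mainly descriptive. It gives no equivalence margin, power or rule for declaring equivalence.

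**The concern.** Matching a standard is evidence of efficacy only if a product with no effect would be expected to fall short of it. Here the bandage is given with at least some routine care, and the yardstick is the result attributed to standard care. If the nitric oxide contributes nothing, and whatever the bandage displaces contributes little, the expected result is the yardstick itself. The phase that 2.1 describes as determining effectiveness could then report equivalence for an inert device.

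The two stated aims also read the same number in opposite ways. A result of 5 of 10 would look like a match under 2.3, 2.4 and 9.0, and like no improvement under 1.3.4. The plan does not say which reading governs.

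**Working it through.** **Inputs.** n = 10 (Summary, 3.2). Reference p0 = 0.50 (2.4). Three assumptions are added because the plan is silent:
- The 50% is a responder rate. It might instead mean an average area reduction of 50%, and then it is no comparator for a proportion.
- A match means at least 5 of 10 responders.
- The true rate with an inert bandage on routine care lies between 30% and 60%.

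The plan states n = 10 without a derivation, so it has no power figure to reproduce.

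**Step 1: how often an inert bandage matches the benchmark.** With p = 0.50 the expected count is 10 × 0.50 = 5. For other rates, P(X ≥ 5) = Σ C(10,k) p^k (1−p)^(10−k) over k = 5 to 10. At p = 0.50 this is (252 + 210 + 120 + 45 + 10 + 1)/1024 = 638/1024 = 62.3%.

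| True rate with inert bandage | P(at least 5 of 10) | P(2 to 8 of 10) |
|---|---|---|
| 30% | 15.0% | 85.1% |
| 40% | 36.7% | 95.2% |
| 50% | 62.3% | 97.9% |
| 60% | 83.4% | 95.2% |

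The last column is the chance of not differing from 50% in a two-sided exact test at 0.05. At p = 0.50 it is 1 − 2(1 + 10)/1024 = 1002/1024. A finding of no significant difference is therefore close to guaranteed across this range and carries little information.

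**Step 2: whether ten subjects can establish equivalence.** The Clopper–Pearson limits for x of n are the α/2 quantile of Beta(x, n−x+1) and the 1−α/2 quantile of Beta(x+1, n−x). For 5 of 10 the 95% interval is 18.7% to 81.3%. The 90% intervals, which serve two one-sided 5% tests, are:

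| Responders | 90% interval |
|---|---|
| 4 of 10 | 15.0% to 69.6% |
| 5 of 10 | 22.2% to 77.8% |
| 6 of 10 | 30.4% to 85.0% |

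None lies within 25% to 75%, and counts further from 5 reach further out. No outcome meets a margin of ± 25 points or tighter. At ± 30 points only 5 of 10 qualifies, with probability 252/1024 = 24.6% when the true rate is 50%.

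**Step 3: whether a margin with more subjects would cure it.** For 80% probability of meeting the margin at a true 50%, the exact calculation needs about 53 subjects for ± 20 points and 214 for ± 10 points. That 80% applies equally to an inert device whose true rate is 50%. A margin and a larger sample repair the precision, but they do not attribute the result to the device.

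**Step 4: whether exceeding 50% would isolate the device.** The exact one-sided 95% lower limit is 49.3% for 8 of 10 and 60.6% for 9 of 10, so at least 9 responders are needed to exceed 50%. An inert bandage at a true 50% gets there with probability (10 + 1)/1024 = 1.1%. If routine care alone gave 70% or 80% in these selected patients (assumed), the probability would be 14.9% or 37.6%. The protection depends on an unsourced figure being right for this cohort.

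**The case against.** **The plan only describes.** Section 2.4 uses that verb, 9.0 is mainly descriptive, no success rule exists, and at least 5 of 10 is a reading supplied here. This stands as a limit on the harm. It does not rescue the conclusion, because the Summary, 2.3 and 9.0 say that equivalence will be determined, and describing 5 of 10 does not support the word.

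**The bandage is an alternative to standard care, not an addition.** Sections 2.2 and 5.11 return subjects whose wounds do not improve to standard techniques, so something is displaced. The debridement sentence is in 5.7 and is not repeated for the treatment visits in 5.8. A reader might infer that the bandage replaces only the dressing, but the documents do not say so. If an active part of standard care is displaced, an inert bandage could fall short, and comparison with the standard would be a legitimate aim. This stands: that an inert device would match the benchmark is conditional. However, the plan never states what is displaced, so the result cannot be interpreted either way.

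**These are non-healing wounds.** Sections 1.3.4 and 6.4 say so. If true, the inert rate could be well below 50%, and at 30% a match occurs only 15% of the time. A reader might infer that an inert device would be called equivalent more often than not; that needs a true rate near 50% or higher. Against this, 4.4 and 4.5 require no ulcer duration, earlier failure of standard care or run-in, so the rate is uncertain in both directions.

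**Any margin would pass an inert device.** A reader might infer this too. At n = 10 it is false: a margin of ± 25 points or tighter passes no device at all.

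**Conclusion.** The equivalence conclusion is wrong as written. Ten uncontrolled subjects on routine care, set beside an unsourced 50%, cannot separate a working bandage from an inert one and cannot establish equivalence. The second failure needs only n = 10 and a proportion as the endpoint. The first needs only that routine care accompanies the bandage without a concurrent control. Its size, a 62% chance of at least 5 of 10, rests on the responder reading of the 50% and on an inert bandage leaving that rate unchanged; over true rates of 30% to 60% the chance runs from 15% to 83%.

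A reader might also infer that adopting the 1.3.4 aim, with a threshold of 9 of 10, would let the trial claim that the device adds to standard care. It would not. It would show at most that the rate exceeds the quoted figure, and the 1.1% error rate holds only if 50% is correct for these patients.

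**What to change.** - Delete the equivalence conclusion from the Summary, 2.3, 2.4 and 9.0, and reconcile these sections with the improvement objective in 1.3.4.
- Report the proportion with at least a 50% area reduction within 2 months, for Noxsano plus routine wound care, with its exact 95% interval. Show the 50% beside it as context only.
- Keep the 2-month window rather than a week-8 reading, and count wounds healed earlier as responders. Under 5.9 and 5.11 a healed wound ends treatment and moves to three-monthly follow-up, so it has no scheduled week-8 measurement.
- State that the device effect cannot be separated from that of routine care, and make no claim of equivalence, superiority or added benefit over standard care.

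The change is wording in four places and one exact interval, with no new data. The price is that the sponsor gives up an equivalence statement and the efficacy result becomes descriptive. A claim about the device itself would need a concurrent control on the same routine care. As an illustration, 50% against 70% or 80% at two-sided 0.05 and 80% power takes 93 or 39 subjects per arm, well beyond this study.

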3.0 STUDY DESIGN

3.1 Study Design Overview

This study is a prospective, interventional, non-randomized, sequential phase study designed to assess the safety and efficacy of the Noxsano Bandage (study device) in subjects with a diabetic lower extremity ulceration and/or arterial insufficiency lower extremity ulceration.

3.2 Subject Population and Sites

Group 1: Initial subjects will be limited to healthy volunteers with intact skin on their lower extremities. Five (5) white subjects and 5 black or African American subjects will be enrolled to evaluate skin differences. Group 1 (healthy volunteers without wounds) will have all follow-up completed and the results assessed before the investigators initiate prior to proceeding to Group 2 (wound care subjects).

Group 2: The subsequent wound care subject study will include 10 subjects from the patient population treated at the OhioHealth Riverside Methodist Hospital Critical Limb Care Center for lower extremity ulceration attributed to diabetes and/or arterial insufficiency.

[figure not shown]
3.3 Expected Study Duration and Subject Participation

Group 1: The initial healthy volunteer safety study will last a total of 4.5 weeks. Healthy volunteers will wear the study device for 3 consecutive days (up to 72 hours), followed by weekly visits for 4 weeks of observation for tolerance, side effects, and/or adverse reactions.

For the purposes of this study, if 2 subjects experience an unacceptable adverse reaction warranting discontinuation of treatment in the opinion of the Investigators during the initial healthy volunteer phase, the study will be halted and Group 2 (and the remainder of the initial phase, if applicable) will not be completed. Allergic reactions and infections at the study device application site will be considered unacceptable at any clinical severity; other adverse reactions will be deemed "unacceptable" by the Investigators on a case-by-case basis dependent upon clinical severity (App. A).

Group 2: The wound care subjects will have twice per week study device applications to a specific ulceration for up to the first 4 weeks of treatment and then weekly reapplication thereafter. For subjects that exhibit any reduction in wound surface area, this application will occur until the wound is healed, or for up to 3 months (whichever occurs first). For subjects that do not exhibit any reduction in wound size at 2 months, application will stop and standard treatment protocols will be pursued. At the conclusion of the treatment window (up to 3 months), subjects will be followed every 3 months for 12 consecutive months for observation of late side effects or adverse reactions (3 months of active treatment, 12 months of follow-up observation, 15 months total).

IRB# 1331496 Page 19 Version 6.0

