5.6 Baseline Procedures

Group 1(Healthy Volunteers): If the subject meets inclusion/exclusion criteria and the informed consent is signed, a 4 x 4 cm segment of healthy, intact skin on the left posterior calf will be shaved by study staff. Study device application will occur within 1-3 days after the Baseline visit in the event that shaving causes irritation.

Group 2 (Wound Care Subjects): Baseline data will be collected, including a routine medical history and physical examination pertaining to study eligibility. The most recent documented baseline HgBa1c and/or ABI values will be collected from the subject's medical record. A baseline photograph and the standard wound measurement using a conventional ruler will be obtained as described in section 5.3. Baseline photographs will be taken with the conventional ruler in place. When possible subjects may proceed immediately to the initial study device application once baseline assessments have been completed.

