Therefore, Group 1 healthy volunteers are more likely to experience adverse events related to hypersensitivity and skin reactions, and are thus being limited to 3 days (up to 72) hours of Bandage wear. It is anticipated that symptoms will manifest within 24-72 hours of application and resolve within 7-10 days of removal, but could take as long as 30 days or more depending on individual skin regeneration. Regarding Group 2 wound care subjects, we expect manifestation and resolution of symptoms on the same timeline, but cannot state decisively as this is the first study in this population. Finally, as itching is a normal consequence of wound healing, we expect this to occur in the majority of Group 2 subjects. No preclinical evidence of significant risk has been demonstrated with the Noxsano Bandage, and therefore is not anticipated or expected during this study.

IRB# 1331496 Page 34 Version 6.0

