7.3 Reporting of Adverse Events

The Principal Investigator or designee is responsible for ensuring that all AEs (both serious and non-serious) observed by the clinical team or reported by the subject which occur after the subject has signed the informed consent are fully recorded in the subject's medical record. Source documentation must be available to support all adverse events.

A critical limb wound care podiatrist is on call 24/7/365. Subjects will be instructed to call the Critical Limb Care Center, and will be seen on an urgent basis as needed based on podiatrist recommendation. The adverse event will be immediately reported to the study Principal Investigator.

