7.3.1 Reporting of Serious Adverse Events

Reporting of SAEs includes reporting of any SAE, any medical device deficiency that might have led to an SAE, and any new finding / update in relation to already reported events.

It is the responsibility of the Principal Investigator or designee to report all SAEs to Noxsano, Inc. (the study device manufacturer) within **2 business days** of discovery or notification of the event.

[figure not shown]
It is the responsibility of the Principal Investigator or designee to report all SAEs according to the IRB of record's policies and procedures.

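### No visible rule spaces the ten Group 1 device applications, so the two-subject halt is not guaranteed to spare any volunteer; and no visible rule follows a non-serious reaction past Day 31

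*Combined protocol and SAP*

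**What the plan says.** The halt rule appears in sections 2.1, 3.3 and 5.7. In 3.3 it applies "if 2 subjects experience an unacceptable adverse reaction warranting discontinuation of treatment in the opinion of the Investigators" during the healthy-volunteer phase; then "the study will be halted and Group 2 (and the remainder of the initial phase, if applicable) will not be completed". The rule is therefore meant to protect Group 1 volunteers not yet treated, as well as to gate Group 2.

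Two timing rules touch Group 1 starts:

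- Section 3.2 places all Group 1 follow-up and its assessment before Group 2.
- Section 5.6 ties each start to that subject's own Baseline: "Study device application will occur within 1-3 days after the Baseline visit in the event that shaving causes irritation".

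Neither sets an interval between subjects. The Protocol Summary anticipates 6 months of enrolment for the study and gives no Group 1 share.

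The device is worn once, for up to 72 hours, with scheduled visits at Day 0 and Day 3 only (5.1, 5.8). Between them, detection depends on the volunteer calling in (5.8, 5.10). Section 7.3 then requires: "The adverse event will be immediately reported to the study Principal Investigator".

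On the course of reactions, section 7.1.1 says: "It is anticipated that symptoms will manifest within 24-72 hours of application and resolve within 7-10 days of removal". It adds that resolution "could take as long as 30 days or more depending on individual skin regeneration". Follow-up visits fall on Days 10, 17, 24 and 31, each ± 2 days. An event's outcome may be recorded as ongoing (7.2.3). Section 7.3.1 asks for "any new finding / update in relation to already reported events", but for serious events. Section 5.11 asks for follow-up of ongoing events at withdrawal.

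**The concern.** A halt at the second reaction prevents exposure only if someone has not yet started. Reactions are expected at 24 to 72 hours and the first scheduled look is at Day 3, so ten starts inside three days would comply fully with the plan and leave the halt nobody to spare. It could then only shorten wear for those still wearing the device. The study is the first in humans. Section 1.3.5 says volunteers receive nitric oxide above normal levels, and that the pig work could not show irritation, which is why Group 1 exists.

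The second gap is smaller. A non-serious skin reaction still present at Day 31 can be closed as ongoing, so the assessment that opens Group 2 would not know how it ended, although the protocol itself foresees reactions that last this long.

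**Working it through.** **The plan's own figure.** Three days of wear plus four weekly visits is 3 + 4 × 7 = 31 days, and 31/7 = 4.43 weeks. This agrees with the stated 4.5 weeks (31.5 days) as one subject's participation.

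**Inputs from the plan.** Ten volunteers, five per skin group (3.2); halt at two reactions (3.3); first scheduled look at Day 3 (5.8).

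**Assumptions, because the plan gives no figures.** The unacceptable-reaction rate p is 5%, 10%, 20% or 30%, independent between subjects. Reactions become known at the Day 3 visit. Ten starts fall uniformly at random over S days. Exposed means started before the second reaction is known.

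**Cohorts run back to back.** Let X_n be Binomial(n, p), with P(X_n ≤ 1) = (1−p)^n + n·p·(1−p)^(n−1).

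- 2+4+4: expected exposed = 2 + 4·P(X_2 ≤ 1) + 4·P(X_6 ≤ 1). At p = 20% this is 2 + 4 × 0.96 + 4 × 0.655 = 8.46. Across the four rates: 9.86, 9.50, 8.46, 7.32.
- 5+5: 5 + 5·P(X_5 ≤ 1) = 9.89, 9.59, 8.69, 7.64.
- 4+6: 4 + 6·P(X_4 ≤ 1). P(X_4 ≤ 1) is 0.986, 0.948, 0.819, 0.652, giving 9.92, 9.69, 8.92, 7.91.

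**No rule against the 2+4+4 rule on the same random arrivals** (simulation). Expected number exposed out of ten:

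| Spread S | Rule | 5% | 10% | 20% | 30% |
|---|---|---|---|---|---|
| 3 days | none | 10 | 10 | 10 | 10 |
| | 2+4+4 | 9.859 | 9.503 | 8.460 | 7.325 |
| | spared | 0.14 | 0.50 | 1.54 | 2.68 |
| 7 days | none | 9.949 | 9.817 | 9.398 | 8.885 |
| | 2+4+4 | 9.859 | 9.504 | 8.464 | 7.325 |
| | spared | 0.09 | 0.31 | 0.93 | 1.56 |
| 14 days | none | 9.873 | 9.557 | 8.645 | 7.657 |
| | 2+4+4 | 9.846 | 9.463 | 8.361 | 7.175 |
| | spared | 0.03 | 0.09 | 0.28 | 0.48 |
| 30 days | none | 9.812 | 9.361 | 8.117 | 6.850 |
| | 2+4+4 | 9.803 | 9.327 | 8.015 | 6.679 |
| | spared | 0.01 | 0.03 | 0.10 | 0.17 |

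**Call-ins, no rule, 3-day spread.** If every reaction is phoned in at 24 to 72 hours, exposure is 9.99, 9.95, 9.83 and 9.65. If every one is phoned in at exactly 24 hours, it is 9.08 at 20% and 8.38 at 30%. Call-ins help, but they do not replace spacing when starts are clustered.

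**Calendar cost.** The mean span from first to last start, without and with the rule, is 2.5 and 6.3 days (S = 3), 5.7 and 6.9 (S = 7), 11.5 and 11.6 (S = 14), and 24.5 and 24.6 (S = 30), before any time for review.

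**Follow-up.** Removal is at Day 3 and the last visit at Day 31: 31 − 3 = 28 days, or 26 to 30 with the ± 2-day window. A reaction lasting 30 days after removal reaches Day 33.

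**The case against.** The strongest reply is that clustered starts are unlikely. The Protocol Summary anticipates 6 months of enrolment at one site. Volunteers come through flyers and a registry, are screened by telephone, must fill a five-plus-five quota and may take no prescription medication. At spreads of 14 days or more the rule spares less than half a volunteer on average, even at an assumed rate of 30%. This stands, and it limits the point to a guarantee. But the 6 months is an expectation with no Group 1 share, and it sets no interval.

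Other safeguards also stand: the 72-hour cap, call-ins, removal for any allergic reaction or infection at the site, and the founders' own wear without apparent harm (1.3.5). None of them secures that a volunteer remains unexposed when the halt fires.

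A reader might infer that "The initial healthy volunteer safety study will last a total of 4.5 weeks" forces near-simultaneous starts, since 31.5 − 31 leaves half a day. The arithmetic fits one subject's participation better, so the documents do not support that reading.

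A reader might also infer that reactions first seen at or after removal do not count, because no treatment is left to discontinue. Section 3.3 counts reactions during the whole healthy-volunteer phase, with no time limit on site allergy or infection, which favours counting them. Section 3.2 also requires completed follow-up to be assessed before Group 2. What remains is a minor clarification.

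On follow-up, expected resolution is 7 to 10 days, so the gap concerns a tail, and an ongoing outcome would be visible at the Group 1 assessment. Its eventual course would not be.

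**Conclusion.** The point holds as a modest, inexpensive improvement. No visible rule spaces Group 1 starts, so whether the halt spares anyone depends on recruitment pace and call-ins. It would be too strong to say that the halt protects nobody, or that all ten will be exposed: that needs starts within 3 days and no reaction reported before Day 3. The expected gain from 2+4+4 is 0.03 to 0.48 volunteers at a 14-day spread and 0.01 to 0.17 at 30 days. It reaches 0.14 to 2.68 only if starts fall within 3 days. All these figures rest on assumed reaction rates, independence and uniform arrivals.

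The follow-up gap is separate: 28 days of planned observation (26 to 30) against a foreseen 30 or more, with no visible rule for non-serious reactions afterwards.

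Two limits apply. The section 10 addendum and Appendix A were not available to this review, and either could hold a relevant rule. The change log says the addendum describes two device-related adverse events, without saying in which group. Nothing can be inferred from that about whether the halt was met. If Group 1 is already complete, the spacing rule matters only for further healthy-volunteer exposure.

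**What to change.** (a) In 3.2 and 5.7, state that Group 1 is treated in at least two cohorts balanced by skin group, for example 2+4+4 or 4+6. No subject in the next cohort starts until the previous cohort's Day 3 SAR questionnaire and photograph have been reviewed against the halt rule. The split is a matter of preference: 5+5 performs similarly but cannot be balanced evenly by skin group. Book each cohort's Baseline so that its 1–3 day window falls after the review.

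(b) In 5.9, state that any reaction present at Day 31 is followed by telephone or visit until resolved or stable, and that its status is reported in the Group 1 assessment before Group 2 starts.

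(c) As a minor clarification wherever the halt rule appears (2.1, 3.3, 5.7), state that reactions first seen at or after removal count toward the two. In 3.3 and 5.1, say that 4.5 weeks is each subject's participation.

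The cost is amendment wording and some scheduling of Baseline visits. Three cohorts need two Day 3 reviews, so at least 2 × 3 = 6 days between first and last start, or about one to two weeks of Group 1 calendar time with review. Little of this is extra if recruitment is already slow. Contacts are added only for reactions still present at Day 31.
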